 Anaphylaxis (severe allergic reaction to a food, bee sting, allergy shot, medication, or other)	 Hypertension (high blood pressure)
 Arthritis	 Nasal Polyps
 Aspirin sensitivity (aspirin causes hives, swelling, or breathing problems)	 Sleep Apnea
 Atopic dermatitis/Eczema	 Stroke
 Chronic bronchitis	 Other (specify): _____
	 Unknown

14. Was spirometry lung function testing performed on this patient in the last 12 months?

[figure not shown]
[figure not shown]
Yes (Record below): Date of most recent spirometry   

[figure not shown]
[figure not shown]
No

[figure not shown]
[figure not shown]
Pre-bronchodilator

[figure not shown]
FVC:  L
 % (predicted)

[figure not shown]
Post-bronchodilator

FVC:  L
 % (predicted)

FEV1:  L
 % (predicted)

FEV1:  L
 % (predicted)

FEV1/FVC ratio 

FEV1/FVC ratio 

Not Available

Not Available

Evidera 138	Site	Page 6 of 7
		
Evidera # 138	Plate # 006	Visit # 001
Participant ID		

15. Please indicate asthma exacerbation history within the prior 12 months:

ASTHMA EXACERBATION HISTORY		 Not applicable				
An asthma exacerbation is defined by a change in asthma control requiring a course of oral steroids (i.e., at least 3 days with at least 10 days between each burst) and/or steroid injection and/or a hospitalization for asthma or emergency department visit for an asthma exacerbation. Importantly, record only the highest utilization for each exacerbation, do not double count exacerbation episodes. If an OCS course was due to a hospitalization, do not record as OCS course but as the hospitalization						
15.1 Number of times in the past 12 months asthma symptoms required an emergency department or urgent care visit (but not an overnight stay in the hospital):						
	ER/urgent care visits (with no overnight hospital stay)	 None				
15.2 Number of times in the past 12 months that there was a worsening in asthma symptoms that required a hospital stay for greater than 24 hours:						
	times admitted to hospital	 None				
15.3 Number of unplanned ambulatory clinic visits due to exacerbation in past 12 months :						

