 ICS only  Low dose  Medium dose  High dose  ICS/LABA  Low dose  Medium dose  High dose  LABA (Single inhaled medicine, not in a fixed-dose combination with an ICS or ICS/LAMA)  LAMA (single inhaled medicine used with or without other inhaled therapies or alone)  ICS/LABA/LAMA (fixed-dose combination)  Leukotriene modifier  Theophylline Preparations  Macrolides Add-on Therapy Biologics  Cinqair (reslizumab)  Dupixent (dupilumab)  Fasenra (benralizumab)  Nucala (mepolizumab)  Xolair (omalizumab)  Other: _____	Rescue Therapy  SABA alone with no maintenance therapy  SABA with maintenance therapy  Primatene Mist as a rescue and no maintenance therapy  Primatene Mist as a rescue with maintenance therapy(s)  ICS+SABA as rescue therapy alone  ICS+SABA as rescue therapy with maintenance therapy(s)  Fixed dose combination fast-acting LABA/ICS alone as rescue  Fixed dose combination fast-acting LABA/ICS as rescue and maintenance therapy  SABA as rescue therapy via nebulizer with other rescue or maintenance therapies  SABA as rescue therapy via nebulizer without other rescue or maintenance therapies
Chronic Oral Corticoid Steroid Therapy  Prednisone _____ mg  QD  QOD  Other (specify): _____	
Note: please see Appendix DD for a description of drugs in each class listed above	

Evidera 138	Site	Page 3 of 5
		
Evidera # 138	Plate # 011	Visit # 003
Participant ID 		

8. Please indicate asthma exacerbation history since last visit:

ASTHMA EXACERBATION HISTORY		 Not applicable

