An asthma exacerbation is defined by a change in asthma control requiring a course of oral steroids (i.e., at least 3 days with at least 10 days between each burst) and/or steroid injection and/or a hospitalization for asthma or emergency department visit for an asthma exacerbation. Importantly, record only the highest utilization for each exacerbation, do not double count exacerbation episodes. If an OCS course was due to a hospitalization, do not record as OCS course but as the hospitalization		
8.1	Number of times since the last visit that asthma symptoms required an emergency department or urgent care visit (but not an overnight stay in the hospital):	 ER/urgent care visits (with no overnight hospital stay)  None
8.2	Number of times since the last visit that there was a worsening in asthma symptoms that required a hospital stay for greater than 24 hours:	 times admitted to hospital  None
8.3	Number of unplanned ambulatory clinic visits due to exacerbation since the last visit:  unplanned visit—Please list dates of the most recent unplanned ambulatory clinic visit below (DD-MMM-YYYY)	 None
a.	 	  None
b.	 	
c.	 	
d.	 	
e.	 	
8.4	How many courses of oral corticosteroids (OCS) was the patient prescribed since the last study visit for asthma exacerbations unrelated to emergency department, urgent care or, unplanned ambulatory clinic visits or hospitalizations?	 0 OCS courses for asthma  1 OCS course only for asthma  2 OCS courses only for asthma  3 OCS courses for asthma  ≥ 4 OCS courses for asthma  patient is on daily OCS
8.5	Date of most current exacerbation:	   unknown

Evidera 138	Site	Page 4 of 5
		
Evidera # 138	Plate # 012	Visit # 003
Participant ID		

9. What is your assessment of the patient's overall asthma control?

- Completely controlled
- Well controlled
- Somewhat controlled
- Poorly controlled
- Not controlled

Part 2. Asthma Checklist (Assess content only)

1. Please check the Asthma Checklist Assess items (page 1) that were considered during the visit:

CONSIDER FOR ALL PATIENTS REGARDLESS OF ASTHMA CONTROL		

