The ASSESS items (in yellow and red) and associated ADJUST items may be appropriate for patients with uncontrolled symptoms and/or risk factors for exacerbations.

To REVIEW RESPONSE, a visit is scheduled within 2 weeks to 6 months to review the patient's response to selected ADJUST items.

[Go to Asthma Checklist](#)

Click the button to open and download the Asthma Checklist.

PRECISION

HOME

ABOUT PRECISION

ASTHMA CHECKLIST

PROVIDER RESOURCES

PATIENT EDUCATION

PATIENT ANIMATIONS

response to selected ADJUST items.

Guidances and Expert Reports

Asthma Checklist: A Tool for Implementing Guidances and Expert Reports in Practice and ASSESS, ADJUST, AND REVIEW RESPONSE are based on key US and other guidances and expert reports including:

- Global Strategy for Asthma Management and Prevention. Global Initiative for Asthma (GINA). 2020. Accessed November 24, 2020. https://ginasthma.org/wp-content/uploads/2020/04/GINA-2020-full-report_-final_-wms.pdf.
- Expert Panel Report 3: Guidelines for the Diagnosis and Management of Asthma (EPR-3). National Institutes of Health; National Heart, Lung, and Blood Institute; National Asthma Education and Prevention Program. 2007. Accessed November 24, 2020. <https://www.nhlbi.nih.gov/sites/default/files/media/docs/asthsumm.pdf>.
- Difficult-to-treat & Severe Asthma in Adolescent and Adult Patients Diagnosis and Management. Global Initiative for Asthma (GINA). 2019. Accessed November 24, 2020. <https://ginasthma.org/wp-content/uploads/2019/04/GINA-Severe-asthma-Pocket-Guide-v2.0-wms-1.pdf>.
- Asthma: Diagnosis and Monitoring of Asthma in Adults, Children and Young People. National Institute for Health and Care Excellence (NICE). 2017. Updated 2020. Accessed November 24, 2020. <https://www.nice.org.uk/guidance/hsg90/resources/asthma-diagnosis-monitoring-and-chronic-asthma-management/pdf-1837687975621>.
- Lung Disease Including Asthma and Adult Vaccination. Centers for Disease Control and Prevention (CDC). Updated 2016. Accessed November 24, 2020. <https://www.cdc.gov/vaccines/adults/rec-vac/health-conditions/lung-disease.html>.
- Recommended Child and Adolescent Immunization Schedule. Centers for Disease Control and Prevention (CDC). 2020. Accessed November 24, 2020. <https://www.cdc.gov/vaccines/schedules/hcp/imz-child-adolescent.html>.

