Sociodemographic Questionnaire. If a follow-up visit (telehealth or in-person) is conducted during the follow-up period, the clinical site will administer the AIRQ® three-month recall version (regardless of timing of follow-up visit). Sites/HCPs will complete a Clinical Case Report Form (CRF) after the initial visit and after the first follow-up visit (if conducted) for each participant. For the initial and first follow-up visit for which patients complete an AIRQ®, HCPs will be required to review the Assess component of the Asthma Checklist and provide their responses on the CRF; while sites are encouraged to use the AIRQ® for any additional follow-up visits during the study and to provide documentation of the AIRQ® scores, additional CRFs will not be completed by the HCPs.

Additionally, Evidera will host a 30-minute conference call with each clinical site for up to four timepoints (touchpoints) to discuss the implementation of PRECISION tools (i.e., frequency of visits to and the number of portable document format (PDF) file views from study website), assess whether sites are meeting their targets for using the telehealth platform, address site questions, and discuss any challenges of implementing the PRECISION program. These meetings will take place at Months 1, 2, 3 (optional), and 6 and will be used to identify any sites that may benefit from participating in a re-training session. The optional Month 3 touchpoint will be based on whether the site has any difficulties with the study.

Study Population: Clinic staff will invite patients age ≥ 13 years with an HCP-confirmed asthma diagnosis who present for a clinic visit (telehealth or in-person) to complete the AIRQ® and participant questionnaires. Each site will aim to recruit approximately 50 to 75 patients with a total sample size ranging from approximately 750 to 1,500 patients. The number of patients recruited from each site may be modified (i.e., able to recruit > 75 patients) to ensure that the target study sample size is obtained.

Inclusion Criteria: Patients must meet all of the following criteria to be eligible for enrollment:

1. ≥ 13 years of age at the time of enrollment
2. Prior diagnosis of HCP-confirmed asthma
3. Able to read, understand, and speak English or Spanish sufficiently to self-complete or be administered the AIRQ™ via telephone, desktop computer, or mobile device (e.g., smartphone, iPad)

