3. ANALYSIS SET

- **All enrolled patients:** All enrolled patients who have completed the initial visit with the AIRQ®
- **Web-survey analysis dataset:** All enrolled patients who complete the initial visit and the web survey
- **Primary care cluster dataset:** All enrolled patients at a primary care site who complete the initial visit and the web survey **CCI**.
- **Exacerbation dataset:** Includes EMR or claims data for enrolled patients who completed the initial visit and have available pre-post exacerbation data.
- **Follow-up analysis set:** All enrolled patients who completed the initial visit with the AIRQ® and have at least one follow-up visit completed in the nine-month implementation period with the follow-up AIRQ®. Patients are not required to have a follow-up visit.
- **HCP analysis set:** All health care providers trained on the study who complete the post-study survey and/or qualitative interview

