[REDACTED] [REDACTED] [REDACTED] [REDACTED] Descriptive statistics (n, %) will be presented for the ACE Questionnaire (item scores) by practice cluster, visit platform, AIRQ® control score, exacerbation history, education level, language, age, sex, and NEPP step level (Table 7 series). Item responses and scores on the patient-reported outcome measures (AIRQ®, CCI [REDACTED] and ACE) will be compared across groups (practice cluster, visit platform, exacerbation history, education level, language, age, sex and NAEPP step level). For continuous variables, ANOVA will be used to compare mean scores across groups; pairwise comparisons between means will be performed using Scheffe's test adjusting for multiple comparisons for more than two groups. For categorical data, chi-square analyses will be used to compare frequencies by groups. No adjustments will be made for multiple groups.

For the follow-up analysis dataset, a patient disposition table will be developed to descriptively characterize the follow-up analysis set in terms of age group, language, race, and education by practice cluster (Table 8a). The mean time to first follow-up visit will be described (n, %) in Table 8b. For the primary care and specialty clusters, the first follow-up clinical CRF will be completed at the patient's first follow-up visit. For the novel cluster sites where patients are receiving multiple asthma coaching sessions, the follow-up clinical CRF will be completed at their final coaching session.

Descriptive statistics (n, %) will be used to describe patients with a follow-up visit by AIRQ® control level at initial visit (Tables 8c). Descriptive statistics (n, %) will also be used to describe patients with a follow-up visit by exacerbation history, education level, language, age, sex, and NAEPP step level at the initial visit (Tables 8d to 8i). Descriptive statistics (n, %) will be used to describe patients with a follow-up visit by HCP actions at the initial visit overall and by practice cluster (Table 8j to 8m).

Clinical characteristics and visit information from the first follow-up visit will be presented using descriptive statistics (n, mean [SD], median, range) (Tables 9a to 9e). Descriptive statistics (n, mean [SD], median, range) will also be used to present the results (overall and by practice cluster) for the first follow-up AIRQ® scores and control levels (Table 10a). AIRQ® scores from the first follow-up

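### Follow-up exacerbations are counted over windows of unequal length with no patient-time, so the raw counts are not comparable between patients or clusters, or with the 12-month baseline

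*SAP*

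**What the plan says.** **Baseline window.** Clinical CRF item 15 (Protocol Appendix I, also reproduced under 4.1.7) reads: "Please indicate asthma exacerbation history within the prior 12 months". The window is the same for every patient.

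**Follow-up window.** Follow-up CRF item 8 (Protocol Appendix J) reads: "Please indicate asthma exacerbation history since last visit". Its sub-items are counts, for example "Number of unplanned ambulatory clinic visits due to exacerbation since the last visit". The form has no field for the length of the window.

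**Timing of the follow-up visit.** SAP section 2 has the 3-month recall AIRQ given "regardless of timing of follow-up visit". The follow-up analysis set in SAP section 3 takes patients who "have at least one follow-up visit completed in the nine-month implementation period with the follow-up AIRQ". SAP section 2 starts that period when the site enrols its last patient, whereas Protocol 6.1.2 gives a follow-up of 6 months after enrolment. For novel sites with several coaching sessions, SAP 5.1 says "the follow-up clinical CRF will be completed at their final coaching session"; primary and specialty care complete the form at the first follow-up visit.

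**Analysis.** SAP 4.1.4.2 lists chart-reported exacerbations among the Follow-up CRF data and takes the first follow-up CRF into the primary analyses. SAP 5.1 then says: "Clinical characteristics and visit information from the first follow-up visit will be presented using descriptive statistics" (n, mean, SD, median, range; Tables 9a to 9e). Table 8b describes the time to first follow-up. SAP 5.1.2 plans elapsed-time groups of 0–3, 4–6 and 7–9 months, but only for AIRQ change and only if numbers allow. No visible passage uses patient-time as a denominator for exacerbations.

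**The concern.** An event count depends on both the rate of events and the time over which they are counted. Here the time is left to the date of a routine return visit. A mean of such counts falls when patients come back sooner, even if their exacerbation rate has not changed.

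Two misreadings follow. A reader who sets the follow-up mean beside the baseline mean sees a drop that a shorter window alone would produce, in a study whose primary objective includes the potential benefits of the program. And a cluster with shorter return intervals looks better than one with longer intervals. The error can also run the other way and hide a real difference in rate.

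**Working it through.** **Inputs.** Baseline window of 12 months: Clinical CRF item 15. Follow-up windows of 3, 6 and 9 months: upper ends of the SAP 5.1.2 elapsed-time groups. Exacerbation rate: none is given in the documents, so 0.5, 1.0 and 1.5 per patient-year are assumed. The plan states no expected count or person-time figure, so there is nothing of its own to reproduce.

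**Step 1: expected count.** With a constant rate r per year and a window of t years, the expected count is r × t. Under a Poisson model, the chance of at least one event is 1 − exp(−r × t).

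| Window | Count, r = 0.5 | Count, r = 1.0 | Count, r = 1.5 | At least one event, r = 1.0 |
|---|---|---|---|---|
| 3 months | 0.125 | 0.25 | 0.375 | 22% |
| 6 months | 0.25 | 0.50 | 0.75 | 39% |
| 9 months | 0.375 | 0.75 | 1.125 | 53% |
| 12 months (baseline) | 0.5 | 1.0 | 1.5 | not used |

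The ratios do not depend on r: 3/9 = one third, 3/12 = one quarter, 9/12 = three quarters.

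**Step 2: same rate, different windows.** Two groups with r = 1.0 and windows of 3 and 6 months have mean counts of 0.25 and 0.50, and 22% and 39% of patients with an event. With an assumed 100 patients per group, a chi-square test on those proportions would be significant about 76% of the time (50% at r = 0.5, 87% at r = 1.5). The visible SAP lists no such test for the Table 9 series, so this only shows how large the artefact can be.

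**Step 3: different rates, same count.** Rates of 0.5 over 6 months and 1.0 over 3 months both give 0.25 (0.5 × 0.5 = 1.0 × 0.25). A two-fold difference in rate disappears.

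**Step 4: do the counts still carry risk?** In a simulation, patient rates followed a gamma distribution (mean 1 per year, shape 0.5 to 2) and windows were uniform from 2 weeks to 9 months. The squared correlation of the count with the true rate was 0.37 down to 0.14, and with the window 0.05 up to 0.08. So individual counts track risk more than window, but the mean is still displaced: the raw mean was 0.39 for a true rate of 1.0. Total events divided by total patient-time returned 1.00.

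**The case against.** **Table 9 content.** SAP 5.1 does not name exacerbations as content of Tables 9a to 9e, and no table shells are available. This stands: their presence is an inference. It is supported by SAP 4.1.4.2, and by SAP Appendix B, which lists N9b beside N4c, N8d and N10c among novel-site tables dropped for lack of telehealth, medical-record history or other data. By SAP numbering, N4c, N8d and N10c are the exacerbation-history tables. The content of N9b itself is not stated.

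**Clusters.** A reader might infer that planned cluster differences will be window artefacts. The documents do not go that far. The SAP does not say that Tables 9a to 9e are split by cluster, although Protocol 5.1 summarises clinical characteristics by site and cluster. Appendix B omits the 9 series from its list of between-cluster tests and shows the novel sites, the only ones with a different CRF timing rule, in separate tables. Nothing shows that return times differ between primary and specialty care.

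**Pre/post claim.** A reader might also infer that the plan will present a spurious fall from baseline. The planned pre/post comparison (Protocol 6.1.2) uses a separate form covering 12 months after the initial visit, for consenting patients at selected sites. No visible passage sets Follow-up CRF counts against baseline. That form does not, however, correct the follow-up counts of other patients.

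**Size.** Quoting a range from 2 weeks to 9 months, about 20-fold, would overstate the problem. The 2-week figure comes from Asthma Checklist advice ("a visit is scheduled within 2 weeks to 6 months to review the patient's response to selected ADJUST items", Protocol Appendix K) and is not a study window. Nor do the counts reflect window length instead of risk; Step 4 shows that they mix the two.

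**Already handled, or redacted.** Table 8b reports time to follow-up, but not as a denominator. The exploratory outcomes and methods are blacked out and may treat exacerbations differently.

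**Limits of a rate.** Exacerbation is a listed reason for the follow-up visit, so the window can depend on the outcome, and dividing by time does not remove that. The oral steroid item has an open top category and a daily-use option, so it is not an exact count. Items 8.1 to 8.3 refer to the last visit but 8.4 to the last study visit. All three points stand and shape the fix.

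**Conclusion.** The concern holds in a limited form. The follow-up window is uncontrolled and no patient-time is specified, so raw follow-up counts mix rate with window length. They are not comparable between patients or clusters, or with the fixed 12-month history. At any constant rate, a 3-month window gives one third of the 9-month count and one quarter of the 12-month count.

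This rests on two assumptions: that Tables 9a to 9e include the Follow-up CRF exacerbation counts, and that nothing in the redacted text already supplies a rate. The ratios assume a constant rate; the absolute counts and percentages in the working also rest on the assumed rates. The tables are descriptive, and exacerbation frequency at follow-up is not a visible primary or secondary outcome. It is therefore a worthwhile, inexpensive improvement in reporting and no threat to the study's main conclusions.

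**What to change.** In SAP 5.1, for the Table 9 series:

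- Report emergency or urgent care visits, admissions and unplanned clinic visits as events per patient-year with 95% CIs, using the days between the visit dates on the Clinical CRF and the Follow-up CRF.
- Show the distribution of window length overall, and by cluster wherever clusters are shown.
- Report oral steroid courses by category within the elapsed-time groups of SAP 5.1.2 (0–3, 4–6, 7–9 months). Add a later group if any visit falls beyond 9 months, which the SAP's start date for the period allows.
- State that the last visit is taken to be the initial study visit. SAP Appendix B reports one follow-up visit per patient, which fits this reading, but say how earlier coaching sessions at novel sites are treated.
- Show results with and without follow-up visits whose recorded reason is an exacerbation.
- Do not set raw follow-up counts beside the 12-month baseline counts.

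The 6-month and nine-month statements of the follow-up period should also be reconciled.

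The cost is SAP wording, one derived variable and a few table rows. Both visit dates are already collected. What remains is some bias from exacerbation-triggered visits, which the rate does not remove and the with/without display only makes visible.
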